1.0 INTRODUCTION

This Statistical Analysis Plan (SAP) provides a comprehensive and detailed description of strategy and statistical technique to be used to realize the analysis of data for Viatris protocol CYST-SLZ-7001, “Real-world evidence observational study to evaluate performance and safety of intravesical sodium hyaluronate (Cystistat®) in the treatment of patients with interstitial cystitis (IC)/bladder pain syndrome (BPS)”.

The reader of this SAP is encouraged to also read the Clinical Investigation Plan (Protocol) for details on the conduct of this study and the operational aspects of clinical assessments and timing for completing a patient in this study. The purpose of this SAP is to outline the planned analyses to be completed to support the completion of the Clinical Study Report (CSR) for protocol CYST-SLZ-7001. The planned analyses identified in this SAP will be included in regulatory submissions if applicable and/or future manuscripts. In addition, exploratory analyses not necessarily identified in this SAP may be performed to support the clinical development program. Any post-hoc, or unplanned, analyses which are not identified in this SAP and will be performed, will be clearly identified in the respective CSR.

2.0 DESCRIPTION OF THE PROTOCOL

2.1 Protocol Number

CYST-SLZ-7001

2.2 Protocol Title

Real-world evidence observational study to evaluate performance and safety of intravesical sodium hyaluronate (Cystistat®) in the treatment of patients with interstitial cystitis (IC)/bladder pain syndrome (BPS).

2.3 Date

Version 1.0, 06APR2022

2.4 Amendment

None

3.0 STUDY OBJECTIVES AND ENDPOINTS

The study objectives and corresponding endpoints are given below:

3.1 OBJECTIVES	3.2 ENDPOINTS
3.1.1 Primary objective	3.2.1 Primary endpoint
To collect data on the performance of Cystistat on patients' overall IC/BPS	Responder rate to treatment at end of treatment or latest at week 12 as indicated by change on a seven-point Patient Global

Form Title: Statistical Analysis Plan

SOP Number: [REDACTED]	Current Version Number & Date: 1.0 & 30NOV2023	Previous Version Number & Document Date: 0.6 & 10NOV2023
---------------------------	---	--

condition at end of treatment or latest at week 12 in routine clinical practice.	Assessment (PGA) scale where the patient is able to evaluate the overall change in her/his IC/BPS condition as markedly improved, moderately improved, slightly improved, no change, slightly worse, moderately worse or markedly worse. For the primary analysis, a responder is defined as a patient who has experienced an improvement on the PGA scale (i.e., PGA evaluated as markedly improved, moderately improved, or slightly improved. In case of slightly improved, patients will only be considered as responder if the question “Did therapy have a positive effect on your life and would you undergo this treatment again?” is answered with “Yes”).
3.1.2 Secondary objectives	3.2.2 Secondary endpoints

 Evaluation of the change of morning voiding volume over time (until month 6) Evaluation of the change of 24-hour urinary frequency and voiding volume (daytime and nighttime) over time (until month 6) Evaluation of change from baseline in Bladder Pain/Interstitial Cystitis Symptom Score (BPIC-SS) (at end of treatment or latest at week 12 and at month 6) Evaluation of patients' overall IC/BPS condition at month 6 (using the same approach as for the primary objective) Evaluation of patients' overall IC/BPS condition at end of treatment or latest at week 12 and at month 6 (using the PGA but with an alternative responder definition) 	
 Morning voiding volume over time (from patient diaries, until month 6). Total number of voids and total voiding volume (daytime and nighttime) over the last 24 hours (from patient diaries, until month 6) Change from baseline to end of treatment or latest to week 12 and to month 6 in Bladder Pain/Interstitial Cystitis Symptom Score (BPIC-SS). Percent responders at month 6 as indicated by improvement on the 7-point Patient Global Assessment (PGA) scale using the same responder definition as for the primary endpoint. Percent responders at end of treatment or latest at week 12 and at month 6 as indicated by improvement on the 7-point Patient Global Assessment (PGA) scale using an alternative responder definition (i.e. a responder is defined as a patient who experiences moderate or marked improvement).

Form Title: Statistical Analysis Plan

SOP Number: [REDACTED]	Current Version Number & Date: 1.0 & 30NOV2023	Previous Version Number & Document Date: 0.6 & 10NOV2023
---------------------------	---	--


 • Evaluation of the change from baseline in bladder pain and urinary urgency on Visual Analogue Scale (VAS) (until month 6) • Evaluation of the change from baseline in quality of life (QoL) on Visual Analogue Scale (VAS) (until month 6) • Evaluation of concomitant IC/BPS and pain medication use (until month 6) • Evaluation of flares (symptom deterioration) (until month 6) • Evaluation of premature termination of treatment • Assessment of tolerability and safety (until month 6) 	
 • Change from baseline to end of treatment or latest to week 12 and to month 6 in bladder pain and urinary urgency on Visual Analogue Scale (VAS) scored from 0 to 100. • Change from baseline to end of treatment or latest to week 12 and to month 6 in quality of life (QoL) on Visual Analogue Scale (VAS) scored from 0 to 100. • Use of concomitant IC/BPS and pain medication count (until month 6). • Occurrence of flares (documented as adverse events) and additional BPIC-SS (at the time of occurrence) (until month 6). • Premature termination of treatment. • Safety assessments: Adverse events and incidents (until month 6).
--	--

4.0 STUDY METHODS

4.1 Study Design and Plan

The present study is a prospective, multicenter, non-interventional study to be conducted in several European countries. It is planned to include approximately 15 study sites. The recruitment will be competitive, with a maximum of approximately 15 patients per site.

4.2 Study Initiation and Completion

The study duration for a patient will be approximately 6 months. The observation period for a patient in this study will end approximately 6 months after start of treatment (irrespective of the duration of treatment). If required, treatment will be continued thereafter under regular medical care.

4.3 Selection of Study Population

Approximately 74 female patients with IC/BPS should be included in the study.

4.4 Study Subject Group

There is one group of treatment in the study:

All patients will receive commercially available Cystistat according to the instructions for use.

Confidential and Proprietary to MEDA Pharma GmbH (A Viatris Company)

Form Title: Statistical Analysis Plan

SOP Number: [REDACTED]	Current Version Number & Date: 1.0 & 30NOV2023	Previous Version Number & Document Date: 0.6 & 10NOV2023
---------------------------	---	--

Cystistat is a clear colourless solution presented in a 50 mL glass vial containing 40 mg sodium hyaluronate. It is manufactured by Mylan [REDACTED] and distributed by third companies in some countries.

4.5 Study Background

Cystistat is supplied as a 50 mL solution containing 40 mg of sodium hyaluronate. It is indicated for the temporary replacement of the GAG layer in the bladder.

Hyaluronan, the biologic form of hyaluronic acid, is found in numerous tissues in the human body. It is part of interstitial fluids in connective tissues and is also an important contributor to surface barriers. Specifically, the importance of hyaluronan as the predominant substance of the GAG layer that protects the urothelial surface of the urinary bladder has been well investigated and documented.

The benefit of GAG substitution therapy in such cases of GAG layer injury has been well documented in several clinical studies since then. Various investigators have reported clinically significant remission rates for intravesical hyaluronan instillation therapy. Several uncontrolled as well as controlled studies have shown remission rates between 60 and 85%. In addition to its efficacy, Cystistat is known to have a good safety profile with a low level of adverse events.

4.6 Study Rationale

Real world evidence observational studies are considered as an expedient tool to reflect the use of a product under real life conditions. However, due to the known difficulties with the diagnosis of IC/BPS, only clinical sites using state of the art diagnostic measures according to current therapeutic guidelines will be selected for this study.

A previous randomized, placebo-controlled trial with Cystistat showed limitations of using a placebo group. In this study, the initial response rate in the placebo group was higher than in the Cystistat group, with a turnaround of results at a later timepoint. Several possible explanations for these unexpected findings have been published. As the most likely reason for the placebo efficacy the possible beneficial effect from the alkalizing placebo solution has been assumed.

Based on these considerations and on the known difficulties in recruiting high number of patients in this indication, an observational real world evidence study was chosen as the best feasible way to collect additional data to demonstrate the benefit/risk profile of Cystistat and compliance with the safety and performance requirements of the Medical Device Regulation (MDR).

4.7 Schedule of Study Events

There are below scheduled visits in this study:

Baseline Visit: Baseline, before first treatment

Treatment Visits 1-11: All visits during Treatment, Week 1 to 11

End of Treatment or latest week 12 Visit: Visit with assessment of primary endpoint latest Week 12 (Month 3)

Follow up-Visit: Follow-up, approximately Month 6

Form Title: Statistical Analysis Plan

SOP Number: [REDACTED]	Current Version Number & Date: 1.0 & 30NOV2023	Previous Version Number & Document Date: 0.6 & 10NOV2023
---------------------------	---	--

4.8 Schedule of Visits and Procedures

	Baseline ⁽¹⁾	During treatment	End of treatment ⁽²⁾	Follow-up ⁽³⁾
Study Day	Before first treatment	Week 1-11 (as per standard of care)	Latest week 12 (Month 3)	Approximately Month 6
Written informed consent	X			
Demography and medical history ⁽⁴⁾	X			
In-/exclusion criteria	X			
Patient Global Assessment of overall IC/BPS condition improvement ⁽⁵⁾			X	X
Assessment of BPIC-SS ⁽⁶⁾	X		X	X
Assessment of VAS ⁽⁷⁾	X		X	X
Instillation of Cystistat ⁽⁸⁾		X	X	(X)
Dispense of diary card ⁽⁹⁾	X		X	
Review of diary card		X	X	X
Collection of diary card			X	X
Assessment of concomitant medications ⁽¹⁰⁾		X	X	X
Assessment of adverse events, incidents ⁽¹¹⁾	X	X	X	X

- 1 Baseline assessments may be performed on the first treatment visit prior to instillation of Cystistat according to routine clinical practice.
- 2 This assessment will be performed on the last treatment day or latest at week 12; if required, treatment will be continued after week 12 under regular medical care.
- 3 Follow-up will be performed as an on-site visit if in accordance with routine clinical practice; if not possible as an on-site visit, the information will be collected remotely (e.g., via phone and postal mail) from the patient.
- 4 Demography and medical history:
 - Patients' demographic and anamnestic background data
 - Diagnostic criteria of IC/BPS diagnosis
 - Previous and current treatments
- 5 Patient Global Assessment of overall IC/BPS condition improvement: To be completed at end of treatment or latest at week 12 and at month 6.
- 6 Bladder Pain/ Interstitial Cystitis Symptom Score (BPIC-SS): To be completed prior to the first treatment, at end of treatment or latest at week 12, and at month 6.

Form Title: Statistical Analysis Plan

SOP Number: [REDACTED]	Current Version Number & Date: 1.0 & 30NOV2023	Previous Version Number & Document Date: 0.6 & 10NOV2023
---------------------------	---	--

- 7 Visual Analogue Scale (VAS) for bladder pain, urinary urgency, and quality of life (QoL): To be completed prior to first treatment, at end of treatment or latest at week 12, and at month 6.
- 8 Instillation of Cystistat: Cystistat will be instilled into the bladder according to the instructions for use; the regimen and duration of treatment will depend on the investigators' discretion; each instillation of Cystistat until month 6 will be recorded in the eCRF; the observation period for this study will end approximately at month 6 (irrespective of the duration of treatment); if required, treatment will be continued after month 6 under regular medical care.
- 9 Diary card: The following assessments are to be filled out by the patient:
 - Morning voiding volume once a week, preferably on the treatment day (until end of treatment or latest week 12) and once at month 6
 - Urinary voids and the respective volumes over a period of 24 hours once a week, preferably starting the day before the treatment day (until end of treatment or latest week 12) and once at month 6
 - Use of concomitant IC/BPS medication, pain medication, and other relevant concomitant medication (until month 6)
 - Adverse events (until month 6)
- 10 The use of concomitant IC/BPS medication, pain medication, and other relevant concomitant medication will be recorded; it is not required to collect all concomitant medication.
- 11 Adverse events and incidents will be recorded after the first instillation of Cystistat; prior to first instillation of Cystistat only adverse events will be recorded.

5.0 GENERAL CONSIDERATIONS FOR STATISTICAL ANALYSIS

All analysis will be based on CDISC compliant AdAM data (IG version: 1.1) derived from SDTM datasets (IG version 3.3).

The descriptive statistics for continuous variables will be presented with number (n) of non-missing observations, number of missing observations (nmiss), mean, standard deviation (SD), minimum, 5% percentile (P5), lower quartile (Q1), median, upper quartile (Q3), 95% percentile (P95) and maximum (range). For categorical data, number (n) and percentage of observations in the various categories of the endpoint will be presented, where percentage will be based on the total number of patients in the respective population or analysed subgroup if not stated otherwise. Individual patient data listings will also be provided. Depending on the study population, data compiled up to the point of discontinuation will be used for analysis. Subjects who are withdrawn prematurely from the study treatment will be included in all analyses (up to the date of withdrawal), regardless of the duration of treatment.

5.1 Sample Size Determination

Approximately 74 patients (including approximately 10% dropouts before end of treatment or latest week 12), are planned to be included in this study.

[REDACTED]

[REDACTED]

Form Title: Statistical Analysis Plan

SOP Number: [REDACTED]	Current Version Number & Date: 1.0 & 30NOV2023	Previous Version Number & Document Date: 0.6 & 10NOV2023
---------------------------	---	--

Accounting for approximately 10% dropouts before end of treatment or latest week 12, further 7 patients and a total of 74 patients will be included in this study.

5.2 Analysis Population**5.2.1 Enrolled population**

The enrolled population includes all patients that have signed the ICF for this study.

5.2.2 Safety (SAF) population

All enrolled patients confirmed by the investigator and who received at least one instillation of Cystistat.

5.2.3 Full analysis set (FAS) population

All patients of the SAF who have at least one post baseline assessment of primary or secondary efficacy endpoint.

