8.2 Populations for Analyses

Safety (SAF) population: All enrolled patients who received at least one instillation of Cystistat and validity of data is confirmed by the physician.

Full analysis set (FAS) population: All patients of the SAF, who have at least one post baseline assessment.

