5.11 Methods for Withdrawals, Missing Data

Subjects who are withdrawn prematurely from the study treatment will be included in all analyses (up to the date of withdrawal), regardless of the duration of treatment. The analysis will be done on observed data only, no imputation will be done for missing values.

5.12 Unscheduled visits and Early termination Visit.

As this is a real-life study, no fix visit schedule is foreseen. Therefore, also unscheduled visits are not applicable.

If the patient terminates early, withdraws or is withdrawn, the reason for early termination/withdrawal will be recorded.

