7.0 EFFICACY ANALYSES

The efficacy analyses will be performed on all the subjects in Full Analysis Set (FAS) if not stated otherwise.

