The Proc mixed procedure of SAS will be used to compare the change from baseline for Bladder Pain/Interstitial Cystitis Symptom Score (BPIC-SS) by adjustment of continuous baseline values.

The following secondary endpoints will be analyzed and reported like the analysis method and reporting of the primary endpoint as described above:

- Percent responders at month 6 as indicated by change on the 7-point Patient Global Assessment (PGA) scale using the same responder definition as for the primary endpoint.

Form Title: Statistical Analysis Plan

SOP Number: [REDACTED]	Current Version Number & Date: 1.0 & 30NOV2023	Previous Version Number & Document Date: 0.6 & 10NOV2023
---------------------------	---	--

- Percent responders at the end of treatment or latest at week 12 and at month 6 as indicated by change on the 7-point Patient Global Assessment (PGA) scale using an alternative responder definition (i.e. a responder is defined as a patient who experiences moderate or marked improvement).

The following secondary endpoints will be presented by summary statistics:

- Counts and percentages will be presented for occurrence of flares (documented as adverse events) and descriptive statistics will be presented for additional BPIC-SS (at the time of occurrence) (until month 6) by summary statistics.
- Number and percentage of premature termination of treatment will be presented by using frequency tables.
- Use of concomitant IC/BPS and pain medication count (until month 6) will be presented by using frequency tables.

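### Premature termination defaults to the FAS, so treated patients who stop and leave no post-baseline efficacy assessment can drop out of the termination rate

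*SAP*

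**What the plan says.** Premature termination of treatment is a listed secondary endpoint (Protocol 2.2.2; SAP 3.2.2). SAP 7.2 describes its analysis in one line: "Number and percentage of premature termination of treatment will be presented by using frequency tables". No population is named there. SAP 7.0 supplies the default: "The efficacy analyses will be performed on all the subjects in Full Analysis Set (FAS) if not stated otherwise". Under SAP 5.0 the "percentage will be based on the total number of patients in the respective population or analysed subgroup if not stated otherwise".

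The FAS in SAP 5.2.3 is: "All patients of the SAF who have at least one post baseline assessment of primary or secondary efficacy endpoint". Protocol 8.2 is looser, asking for a post-baseline assessment of any kind: "All patients of the SAF, who have at least one post baseline assessment". The SAF in SAP 5.2.2 has no post-baseline condition: "All enrolled patients confirmed by the investigator and who received at least one instillation of Cystistat".

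SAP 5.11, like SAP 5.0, says that patients withdrawn early from study treatment "will be included in all analyses (up to the date of withdrawal), regardless of the duration of treatment".

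**The concern.** The termination table should show how often treated women give up treatment. Under the default it is computed in a set that requires efficacy data after baseline, and those data are least likely to exist for the women who stop first.

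The route by which a patient is lost is plausible. In the schedule (SAP 4.8), the PGA, the BPIC-SS and the VAS are first due after baseline at end of treatment or week 12. Before that, the routine efficacy source is the paper diary, which the site reviews and transcribes at the next treatment visit (Protocol 6.2). A woman instilled once who does not return and cannot be reached is classed as lost to follow-up (Protocol 6) and will usually have no efficacy entry after baseline. Protocol 7.1.8 still requires the date of her last treatment and the reason for stopping to be documented. The data needed to count her would be in the database, yet the default population may leave her out.

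At stake is a tolerability-type rate in a single-arm study that is meant to support the benefit-risk profile (Protocol 3.2). Any distortion favours the device.

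**Working it through.** **Inputs.** Planned total 74, of whom 7 are added for approximately 10% drop-out before end of treatment or week 12 (SAP 5.1). The base of 67 is implied as 74 − 7; its derivation is blacked out and was not recomputed.

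**The plan's own figure.** 67 × 1.10 = 73.7, rounded up to 74, which matches. Dividing instead, 67 / 0.90 = 74.4, rounded up to 75, is within one patient. The 74 is not in dispute.

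**Formulas.** Let N be the number treated, T the number who terminate prematurely, and k the number of those with no qualifying post-baseline assessment (0 ≤ k ≤ T).

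- SAF rate = T / N
- FAS rate = (T − k) / (N − k)
- Difference = T/N − (T − k)/(N − k) = k(N − T) / [N(N − k)]

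The difference is never negative, so the FAS rate cannot exceed the SAF rate. It is zero when k = 0.

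**Assumptions.** All 74 are treated (N = 74). The documents forecast neither T nor k. T = 7 borrows the drop-out allowance as a proxy; T = 15 shows a heavier case.

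| T | k | SAF rate | FAS rate | Difference (points, from unrounded rates) |
|---|---|---|---|---|
| 7 | 0 | 7/74 = 9.5% | 7/74 = 9.5% | 0.0 |
| 7 | 1 | 9.5% | 6/73 = 8.2% | 1.2 |
| 7 | 2 | 9.5% | 5/72 = 6.9% | 2.5 |
| 7 | 3 | 9.5% | 4/71 = 5.6% | 3.8 |
| 7 | 7 | 9.5% | 0/67 = 0.0% | 9.5 |
| 15 | 3 | 15/74 = 20.3% | 12/71 = 16.9% | 3.4 |

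The row with k = 7 is a bound, not an expectation: it needs every terminator to leave nothing behind.

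**Consistency of the text.** SAP 5.2.3 with 7.0 removes a treated terminator who has no efficacy data. SAP 5.0 and 5.11 keep her in all analyses however short her treatment. Neither place says which prevails.

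Flares have a related problem. They are recorded as adverse events (Protocol 7.1.7) and so are tabulated on the SAF under SAP 8.0 and 8.1. SAP 7.2 counts them again, by default on the FAS. The same events can thus appear over two denominators.

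**The case against.** Several points on the other side have force.

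- **Data are sought at withdrawal.** Protocol 6.5 asks sites to try to obtain the diary, BPIC-SS, PGA and VAS from patients who terminate or withdraw. Any one of these, with post-baseline content, brings the patient into the FAS. This stands, and it limits the problem to patients from whom nothing is obtained. It cannot help with a patient who is unreachable.
- **The termination record may itself qualify.** Premature termination is a listed secondary endpoint and is analysed under a secondary efficacy heading. On that reading every documented terminator is in the FAS, SAP 5.0 and 5.11 are honoured, and there is no bias. The reading is open, but it would leave the FAS condition with little to do, and SAP 5.2.3 does not say which endpoints count. Naming the SAF settles the matter under either reading.
- **Other tables cover part of the ground.** Flares appear among the adverse events on the SAF. Concomitant IC/BPS and pain medication is tabulated in SAP 6.2, outside the section 7 default, and is summarised under the safety analyses in Protocol 8.3.7.1. Stops caused by adverse events show up through the action-taken table (SAP 8.1; categories in Protocol 10.3.5). This stands; what has no explicit SAF table is the overall termination count.
- **The analyses are exploratory.** All analyses are exploratory (Protocol 8.3), and patient listings are provided (SAP 5.0). This bears on priority, not on whether the denominator is right.

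**Conclusion.** The point holds in a limited form. By default the termination rate is computed in a set from which treated terminators without post-baseline efficacy data can be missing. Any resulting error runs downward only. With 7 terminators among 74 treated, it is 1.2 points for one such patient, 2.5 for two and 3.8 for three. It is zero if every terminator has a qualifying assessment or if the termination record counts as one. The sizes rest on the drop-out allowance as a proxy, on all 74 being treated, and on an unknown k.

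Three stronger readings are tempting but not supported:

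- A reader might infer that every woman who quits after the first instillation disappears. Stopping does not exclude her; having no qualifying assessment does.
- A reader might infer that the SAP deliberately assigns termination to the FAS. No sentence does so; it follows from the default in SAP 7.0.
- A reader might infer that the responder rate is shown to be inflated. SAP 7.1 divides by all FAS patients, so a FAS member without a PGA already counts as a non-responder. For treated patients outside the FAS, part of SAP 7.1 on additional analyses is redacted and may already give a rate over all treated patients. If it does not, the effect with one such patient and an assumed 47 responders is 47/73 = 64.4% against 47/74 = 63.5%.

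This is a cheap improvement, not a threat to the primary result.

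**What to change.** 1. In SAP 7.2, state that premature termination is tabulated on the SAF (treated patients, confirmed by the investigator as SAP 5.2.2 requires), overriding the default in 7.0.
2. In SAP 7.2, use the SAF for the flare count as well, so that it agrees with the adverse event tables in section 8.
3. In SAP 5.2.3, list the assessments that admit a patient to the FAS, and word this consistently with SAP 5.0 and 5.11.
4. Add a responder rate over all treated patients in SAP 7.1 only if the redacted text there does not already provide one.

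The cost is a few sentences in the SAP, with no new data. The drawback for the sponsor is that the reported termination rate may be slightly higher.
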